9.2 Discontinued Subjects

Any subject is free to discontinue his/her participation in this study at any time and for whatever reason, specified or unspecified, and without prejudice.

An Investigator may decide to discontinue a subject from the study for safety reasons or when it is in the best interest of the subject. Galderma Laboratories, L.P. may also decide to prematurely terminate or suspend the study or the participation of a subject in the study. All data gathered on the subject prior to termination should be made available to Galderma Laboratories, L.P.

Criteria for the discontinuation of a subject during the study will include the following:

- Adverse Event
- Lack of Effect
- Pregnancy
- Subject Request
- Protocol Violation
- Lost to Follow-up
- Any unmanageable factor, in the Investigator's opinion, that may significantly interfere with the protocol or interpretation of results.

Protocol Version: 04

This document contains confidential, proprietary information.

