4. BACKGROUND AND RATIONALE

During aging, the skin undergoes significant changes that are often characterized by dermal thinning, redistribution of fat, and loss of skin elasticity and collagen.^{1, 2} Various factors can considerably accelerate this aging process, including environmental exposure, leading to rhytids, wrinkles, and skin laxity. There has been an increase in popularity of soft-tissue injectables as they are non-invasive and are effective for restoring lost volume and for correcting contour deficiencies to the aging face.³ Among them are two well-known injectable agents: Sculptra® (Galderma, New Jersey, USA) and Radiesse® (+) (Merz Pharmaceutical, Wisconsin, USA). Sculptra® is a poly-L-lactic acid (PLLA) biostimulator and Radiesse® (+) is a calcium hydroxylapatite (CaHA) filler. Both treatments are currently FDA-approved in the United States for correction of facial wrinkles and folds. Both provide a delayed but progressive volumizing effect by stimulating the regeneration of endogenous collagen overtime.^{4, 5}

As such, a similar mechanism of action of these injectables represents an interesting line of examination, particularly in the context of cellular activities occurring at the genomic level that contributes to neocollagenesis and potentially other structural integrity of the extracellular matrix. This study is conducted to examine the effect of PLLA and CaHA injectables in the treatment of nasolabial folds (NLFs).

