6. SELECTION AND DISPOSITION OF STUDY POPULATION

6.1 Number of Subjects

An appropriate number of subjects meeting inclusion/exclusion criteria listed below will be enrolled on the study to achieve maximum 20 subjects who complete the study as planned.

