7.6 Treatment Dosage and Mode of Administration

The injection technique (skin disinfection material, type of syringe, type and gauge of the intradermal needle, penetration angle, depth) will be the technique customarily used by the Investigator. The type of gauge of the injection needle will be recorded in the CRFs.

PLLA: two treatment sessions at 4-week interval with the first treatment at Visit 1 and the second treatment at Visit 3. Each treatment session will be consisted of multiple deep dermal injections, up to 9 mL/session (or up to 4.5 mL/NLF/session), into the left and right NLFs of each subject according to the IFU. The treatment amount for each PLLA subject will be determined at the Investigator discretion to achieve an optimal correction. Within each PLLA subject, the amount of each treatment needs to be equal at the left and right NLFs because of the identical WAS scores. The treatment volume injected during each treatment session for each subject will be recorded in the CRFs.

CaHA: up to two treatment sessions at 4-week interval with the required first treatment at Visit 1 and an optional second treatment at Visit 3 to achieve an optimal cosmetic correction. Each treatment session will be consisted of multiple subdermal injections, up to 1.5 mL/session (or up to 0.75 mL/NLF/session), into the left and right NLFs of each subject according to the IFU. The second treatment is optional and will be determined based on the Investigator assessment. If the subject needs a second treatment, an appropriate amount will be determined at the Investigator discretion to achieve an optimal outcome. The amount of each treatment needs to be equal at the left and right NLFs because of the identical WAS scores. The treatment volume injected during each treatment session for each subject will be recorded in the CRFs.

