10.3 Punch Biopsy Collection and Analysis

At baseline/day 0 and day 84, subjects will participate in a 3-mm punch biopsy procedure (post-photography and pre-treatment). Each subject will have 1 biopsy at one side of the NLF (based on the pre-determined randomization) at baseline and 1 biopsy at the other side of the NLF at day 84; total of 2 biopsies per subject at both timepoints.

Biopsies will be obtained using standard sterile technique after an intradermal local anesthesia and treated with topical antibiotic and sterile dressing in routine fashion (see Appendix I: Biopsy Procedure and Post-Care).

The biopsy specimens will be immediately transferred into RNAlater solution and stored at room temperature for 4 hours and then moved to 4°C. Collected biopsy samples will be sent to the following address for gene expression analysis on icepack (4°C).

The biopsy sample will contain the subject number/identification (baseline and day 84), product information, and any other relevant information needed to identify the samples post-analysis.

Attn: [name]
Genemarkers, LLC
[name]
[name]
[contact]

Gene expression analysis will be performed via qPCR processing using a panel of biomarkers related to scar tissue formation, collagen, elastin, extracellular matrix integrity, epidermal barrier, anti-aging, antioxidant, cell renewal/regeneration, inflammation, growth factor, and hydration among others.

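### Section 9.2 allows discontinuation for lack of effect without follow-up to Day 84, so poor responders can be lost from both endpoints and replaced

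*Combined protocol and SAP*

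**What the plan says.** Five parts of the combined protocol and SAP bear on this point.

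- **Section 9.2** introduces its list with "Criteria for the discontinuation of a subject during the study will include the following". The second item is "Lack of Effect". No definition, threshold, assessor or earliest time is given, and nothing says that a subject so discontinued still attends the Day 84 visit.
- **Section 4** says of the two products: "Both provide a delayed but progressive volumizing effect by stimulating the regeneration of endogenous collagen overtime".
- **Section 7.6** gives PLLA as "two treatment sessions at 4-week interval with the first treatment at Visit 1 and the second treatment at Visit 3" and CaHA as "up to two treatment sessions at 4-week interval with the required first treatment at Visit 1 and an optional second treatment at Visit 3". The flow chart in Section 9 agrees: no injection is scheduled after Visit 3 (Day 28) in either arm.
- **Sections 10.2 and 10.3** set the outcome times. Imaging is at Days 0, 28 and 84. After the baseline biopsy there is "1 biopsy at the other side of the NLF at day 84", and no other post-treatment tissue is taken.
- **Sections 6.1 and 11** decide who is counted. Subjects "will be enrolled on the study to achieve maximum 20 subjects who complete the study as planned", which the synopsis splits as 10 per product group. Section 11 restricts every statistical analysis to completing subjects.

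**The concern.** Lack of effect is a statement about the outcome. If it is a ground for leaving the study, whether a subject has Day 84 data can depend on how well that subject responded. For products whose effect is described as building up over time, little visible change at Day 28 is compatible with the expected course. After the Visit 3 injections there is no study treatment left to stop, so a later discontinuation on this ground only loses Day 84 data.

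The rule works together with two others. The completers-only rule drops even the Day 28 image of such a subject, and enrolment towards a target number of completers lets another subject fill the place. The result could be a set of 20 completers, 10 per arm, from which some weak responders have been filtered out.

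This is separate from the choice of analysis set. A broader set could bring back a Day 28 image, but not a Day 84 biopsy or image that was never taken.

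**Working it through.** **No plan figure to reproduce.** The documents give 20 completers without alpha, power, effect size, SD or dropout rate. The check is first a reading of the text, then an illustration of size.

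**Step 1: follow one subject.** Suppose a subject is judged at Visit 3 to lack effect and is discontinued under Section 9.2.

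- Primary objective: the baseline biopsy exists but the Day 84 biopsy does not, so there is no change in expression.
- Secondary objective: the Day 28 image exists but the Day 84 image does not.
- Analysis: the subject is not a completer, so Section 11 excludes the Day 28 image as well.
- Enrolment: Section 6.1 counts completers, so another subject can be enrolled.

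Section 9.2 has the earlier data handed to the sponsor, but no passage brings them into an analysis.

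**Step 2: assumed inputs for size.** Volume change is normal with SD 1 in both arms and the true difference is zero. In one arm 10 + k subjects are enrolled, the k judged lowest leave, and 10 complete. The judgement is made at Day 28 and has correlation r with the Day 84 outcome. None of this comes from the documents except the 10 completers per arm.

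**Step 3: standard error of the difference.** √(1/10 + 1/10) = √0.2 = 0.447 SD.

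**Step 4: shift in the affected arm.** Under normality the shift is r times the shift that would follow from selecting on the Day 84 outcome itself. By simulation that limiting shift is 0.159 SD for k = 1 and 0.275 SD for k = 2. For example, 0.5 × 0.159 = 0.080 and 0.7 × 0.275 = 0.193. Direct simulation gives:

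| k replaced, one arm only | r | Shift (SD) | Shift / 0.447 | Two-sided false-positive rate, nominal 0.05 |
|---|---|---|---|---|
| 1 of 11 | 0.3 | 0.047 | 10.5% | 0.052 |
| 1 of 11 | 0.5 | 0.080 | 17.9% | 0.056 |
| 1 of 11 | 0.7 | 0.112 | 25.1% | 0.061 |
| 2 of 12 | 0.3 | 0.083 | 18.6% | 0.055 |
| 2 of 12 | 0.5 | 0.137 | 30.6% | 0.064 |
| 2 of 12 | 0.7 | 0.192 | 43.0% | 0.077 |

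**Step 5: equal removal.** With one subject replaced in each arm at r = 0.5, the expected difference is zero. Each arm's mean change is still raised by 0.08 SD, and the within-arm test of no change rejects a true null about 6% of the time.

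**Step 6: with the subjects kept.** If they are followed and analysed (k = 0), the bias is zero and the simulated between-arm rejection rate is 0.049 to 0.051.

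For scale, a t-test with 10 per arm has 80% power only for a difference of about 1.32 SD.

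**The case against.** The strongest reply is that this is standard wording that may never be used. Section 9.2 names no threshold, and no visit step triggers removal. Wrinkle grading is done at baseline only (Section 10.1). At Visit 3 the scheduled course is a second PLLA treatment or an optional CaHA touch-up, after which the subject is booked for Day 84. No visit falls between Days 28 and 84. The list also includes loss to follow-up and subject request, so it can be read as categories for the exit form mentioned in Section 12.5. All of this stands against saying that poor responders *are* removed. It does not show that they cannot be, because the lead-in calls the items criteria and no passage keeps such a subject to Day 84.

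Section 6.5.2 does let a subject who has received prohibited therapy stay on, but for safety evaluation only. That provision neither covers lack of effect nor supplies outcome data.

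A reader might also infer more than the text supports:

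- **A larger bias.** Selecting on the Day 84 response itself gives 0.16 SD (1 of 11) or 0.27 SD (2 of 12), up to about 60% of the standard error. That response is unknown when a subject leaves before Day 84, so these are limiting values and not estimates.
- **A biased product comparison in any case.** The expected difference is biased only if removals differ by arm.
- **Loss of the least responsive tissue from the gene comparison.** No passage links visible correction to qPCR expression. The sample is lost, but the direction of any bias is unknown.
- **The same argument for protocol violations.** That item is in the same list, but it does not select on outcome as lack of effect does, so the argument does not carry over.

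**Conclusion.** The point holds as a gap in the rules, not as a prediction of what will happen. Sections 9.2, 6.1 and 11 together permit outcome-dependent loss before Day 84 followed by replacement, and no choice of analysis set can recover the missing Day 84 data.

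For volume, the completers' mean change would be biased upward within an affected arm, and the product difference would be biased if the arms lose different numbers. On the assumptions above the shift is about 0.05 to 0.19 SD, or roughly 10% to 43% of the 0.447 SD standard error. That is modest, and it depends on one or two subjects being replaced in one arm only. For gene expression the primary-endpoint sample is lost, with an effect of unknown direction. The documents do not allow an estimate of how often this would occur. An amendment is still worthwhile, because the Day 84 visit is already scheduled.

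**What to change.** Amend Section 9.2 so that lack of effect alone does not end data collection. A subject so judged stays in follow-up for the scheduled Day 84 image and, if still willing and if it is safe, the Day 84 biopsy. Amend Section 11 so that these data enter the analysis, and reconcile Section 6.1 so that such a subject is not treated as a non-completer to be replaced. Report discontinuations by reason and arm.

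Safety withdrawal and subject request stay as written. The change concerns data collection only; no rule on stopping treatment is proposed.

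The cost is one short amendment, with IRB approval under Section 14.4. No visit, image or biopsy is added to the schedule. The downside is that observed effects may look slightly smaller because poor responders remain in the data.

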10. STUDY ASSESSMENTS

All images taken from the study will be saved and shared to the Sponsor via a data-protected platform.

10.1 Wrinkle Assessment Scale

Clinical grading of NLF will be performed at baseline for screening purpose. The grading will be based on a 6-point Wrinkle Assessment Scale⁶ according to the numerical definitions (describe in Figure 1 below).

- 0 = no visible, minimal wrinkles
- 1 = just perceptible wrinkles
- 2 = shallow, visible wrinkles with a slight indentation
- 3 = moderately deep wrinkles
- 4 = deep wrinkles, well-defined folds
- 5 = very deep wrinkles, redundant folds

[figure not shown]

Figure 1. Wrinkle Assessment Scale of nasolabial folds

10.2 Clinical Photography (Cherry Imaging)

Three (3) dimensional images of the subject's face will be taken at baseline/day 0 (pre-biopsy and pre-treatment), day 28 (pre-treatment), and day 84 (pre-biopsy).

Protocol Version: 04

This document contains confidential, proprietary information.

Protocol GLI.04.US.SL.020

CONFIDENTIAL

Clinic staff needs to ensure subjects to have a clean face with no makeup, no facial hair, and to remove any jewelry from the area to be photographed. Subjects will be provided with a headband to keep hair away from the face. Subjects will be instructed to adopt neutral, nonsmiling expression with their eyes gently closed, and in a relaxed positioned for each scan.

A total of three 3D images will be taken of each subject's face using the Cherry Imaging device (Cherry Imaging, Israel). The Cherry Imaging relies on multi-directional illumination and computer-aided reconstruction of the skin surface in 3D.

Change in volume on each NLF will be analyzed by the Cherry Imaging software.

10.3 Punch Biopsy Collection and Analysis

At baseline/day 0 and day 84, subjects will participate in a 3-mm punch biopsy procedure (post-photography and pre-treatment). Each subject will have 1 biopsy at one side of the NLF (based on the pre-determined randomization) at baseline and 1 biopsy at the other side of the NLF at day 84; total of 2 biopsies per subject at both timepoints.

Biopsies will be obtained using standard sterile technique after an intradermal local anesthesia and treated with topical antibiotic and sterile dressing in routine fashion (see Appendix I: Biopsy Procedure and Post-Care).

The biopsy specimens will be immediately transferred into RNAlater solution and stored at room temperature for 4 hours and then moved to 4°C. Collected biopsy samples will be sent to the following address for gene expression analysis on icepack (4°C).

The biopsy sample will contain the subject number/identification (baseline and day 84), product information, and any other relevant information needed to identify the samples post-analysis.

Attn: [name]
Genemarkers, LLC
[name]
[name]
[contact]

Gene expression analysis will be performed via qPCR processing using a panel of biomarkers related to scar tissue formation, collagen, elastin, extracellular matrix integrity, epidermal barrier, anti-aging, antioxidant, cell renewal/regeneration, inflammation, growth factor, and hydration among others.

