5. STUDY OBJECTIVES AND CLINICAL HYPOTHESIS

5.1 Study Objectives

The primary objective of this study is to compare gene expression stimulated by a semi-permanent filler and a biostimulator via punch biopsy.

The secondary objective of this study is to assess and compare volume change in the NLF via clinical photography.

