7.5 Method of Treatment Assignment

Before the start of the study, a randomization list will be prepared by the Sponsor utilizing a computer-generated software. This will randomly assign the study product to each enrolled subject and the NLF side for punch biopsy.

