8.2 Subject Identification

Enrolled subjects will be assigned a number that will uniquely identify every subject on the study. The numbers will remain with the subject throughout the study and should be used in all references to the individual in this study.

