9.1 Visits and Examinations

9.1.1. Visit 1 (Screening/D0/Baseline)

1. Subjects will report to the testing clinic at D0 for baseline screening.
2. Subjects will be screened and qualified on the basis of the subject inclusion and exclusion criteria. Subjects failing to meet criteria will be dismissed from the study.

Protocol Version: 04

This document contains confidential, proprietary information.

Protocol GLI.04.US.SL.020

CONFIDENTIAL

3. Prior to beginning of any study related activities, subjects will be informed about the purpose and nature of the study, the expected post-treatment events, and the potential risks involved with the treatments.
4. Subjects will be given an informed consent form, HIPAA form, and photography release form to read.
5. Once subjects have completed reading, they will be interviewed to ensure their understanding of the aforementioned forms and be given the opportunity to ask any study related questions.
6. Subjects who agree to sign the aforementioned forms will be asked to complete a demographic information, medical history form, and concomitant medication form. Subjects declining to sign any of the forms will be dismissed from the study.
7. Female subjects will need to perform UPT to confirm childbearing potential.
8. Subjects will be assigned to a treatment group and side of punch biopsy at the NLF based on the predetermined computer-generated randomization.
9. Subjects will participate in the following procedures completed by the Investigator or a trained clinic staff:
 - a. 3D clinical photography by Cherry Imaging of full face as described in section 10.2
 - b. A 3-mm punch biopsy at the assigned side of the NLF as described in section 10.3
10. Investigator will then instruct the subjects on the assigned treatment administration procedure and perform the treatment into both left and right NLFs.
11. Investigator or clinic staff will record the details of the administration, amount of each treatment used for each NLF and any subsequent adverse events (AEs) in the CRF.
12. Subjects will be instructed on any standard care post-biopsy and post-treatment, and when to contact the Investigator in case of emerging AEs.
13. Subjects will be scheduled to return to the clinic in 5 days (± 1 day) and dismissed from the clinic.

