11. STATISTICAL ANALYSIS

Data of completing subjects will be included for all statistical analyses. Descriptive statistical summary will be performed including N, mean, median, standard deviations, minimum, and maximum of values at all applicable time points and for both treatments.

Comparison between the study treatments will be made in terms of changes from baseline. The null hypothesis, that the mean change from baseline is equal between the 2 study treatments at post-baseline time point, will be tested using methods described in the Statistical Analysis Plan table.

Protocol Version: 04

This document contains confidential, proprietary information.

Statistical Analysis Plan

Evaluation	Change from Baseline	Comparisons between study treatments	Notes/Interpretation
Volume change by 3D imaging analysis	Paired t-test; If normality fails, a Wilcoxon signed-rank test will be used.	Wilcoxon rank-sum test or sample t-test	A higher value reflects an improvement in skin volume.

Statistical analysis for gene expression will be determined using the relative quantification method.

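### Section 10.3 sends product information with every biopsy to the qPCR laboratory, so the laboratory can know the arm, although subject number plus visit already identifies each sample

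*Combined protocol and SAP*

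**What the plan says.** Section 10.3 sends the punch biopsies to an external laboratory for qPCR and sets the content of the label: "The biopsy sample will contain the subject number/identification (baseline and day 84), product information", together with "any other relevant information needed to identify the samples post-analysis".

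These values serve the main aim of the study. Section 5.1 states: "The primary objective of this study is to compare gene expression stimulated by a semi-permanent filler and a biostimulator via punch biopsy". Section 11 adds: "Comparison between the study treatments will be made in terms of changes from baseline".

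On identification, Section 8.2 says: "Enrolled subjects will be assigned a number that will uniquely identify every subject on the study". On allocation, Section 7.5 says that "a randomization list will be prepared by the Sponsor"; the list assigns the product to each subject and also the side to be biopsied.

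The Synopsis describes a randomized, single-center, comparative study. Neither it nor any other section says that the laboratory is masked, that samples are coded, or that the product is withheld until results are final.

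**The concern.** The laboratory produces the values on which the two products are compared, and under Section 10.3 it can know which product each subject was assigned. The stated purpose of the label is identification, and the product does not appear to be needed for that.

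The plan leaves the laboratory's handling of the data open. For gene expression, Section 11 says only that relative quantification will be used, and its analysis table covers volume change alone. No reference genes, repeat rule, acceptance threshold or exclusion rule is given, and the biomarker panel in Section 10.3 is open-ended. Any such decision could be made with the arm in view. With 10 completers planned per product, a few decisions that lean one way could matter.

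**Working it through.** The plan gives no figure to reproduce here. The check is a count of labels, a reading of the visit sequence, and a short piece of algebra.

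**Inputs**
- 20 completers, 10 per product (Synopsis; Section 6.1). Enrolment may exceed this, since enough subjects are enrolled "to achieve maximum 20 subjects who complete the study as planned".
- One biopsy at baseline and one at day 84, so 2 per subject (Section 10.3).
- One unique number per subject (Section 8.2).
- Product assigned per subject (Section 7.5) and injected into both folds (Section 9.1.1, step 10).

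**Step 1. Is the product needed to identify a specimen?**

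Specimens: 20 × 2 = 40 (20 baseline, 20 day 84).

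| Label content | Distinct labels for 40 specimens |
|---|---|
| Subject number only | 20 |
| Subject number + visit | 20 × 2 = 40 |
| Subject number + visit + product | 40 |

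The visit is needed. The product adds 40 − 40 = 0 identifiers. The same holds for any number N enrolled: there are at most 2N specimens, and subject number plus visit separates them all.

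**Step 2. Does the product reveal the arm?** Both folds of a subject receive the same product, so naming the product on either specimen names the arm.

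**Step 3. What does the field convey at baseline?** In Section 9.1.1, assignment is step 8, the biopsy is step 9b and the injection follows at step 10: "Investigator will then instruct the subjects on the assigned treatment administration procedure and perform the treatment into both left and right NLFs". The product is therefore known when the baseline specimen is labelled, but the tissue contains none of it. On those 20 specimens the field tells the laboratory only the arm.

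**Step 4. How would a measurement shift reach the result?** Let s be any additive shift in the measured value that comes from knowing the arm. The bias in the between-product difference of changes is

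B = (s_PLLA,84 − s_PLLA,0) − (s_CaHA,84 − s_CaHA,0).

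- Same shift s at both visits of one arm, none in the other: B = (s − s) − 0 = 0.
- Shift s at day 84 of one arm only: B = (s − 0) − 0 = s.

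Change from baseline therefore removes a shift common to both visits of an arm, and passes on in full a shift that differs between visits. This assumes a scale on which shifts add, such as Ct or log expression; Section 11 names no scale. The documents give no value for s.

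**Step 5. Selective exclusion.** The algebra in Step 4 does not cover this route. Excluding a specimen changes which subjects are averaged, and the effect does not cancel. A change from baseline needs both specimens of a subject, so rejecting one removes 1 of 10 subjects, or 10%, from that arm's change data.

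**The case against.** The strongest reply is that the plan promises no blinding, so nothing here contradicts it, and that qPCR is an instrument reading and not a subjective grade. Both points are true. They limit the finding to an avoidable weakness of unknown size. They do not remove it: unmasked injection does not require an unmasked laboratory, and decisions to repeat, accept or exclude a sample, or to choose reference genes, involve judgment that the plan leaves unconstrained. The laboratory may have its own procedures for these, but the plan does not cite any.

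A second reply is that identifying samples after analysis could mean assigning results to treatment groups, and that the laboratory may perform that comparison. Section 11 does not say who does. If it is the laboratory, it needs the key at some point, but not while it is producing the data. Within-subject change needs only subject and visit, and the key can follow once the values are fixed.

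Third, the term for the product field is not defined. The assigned product is its natural meaning, but the safe statement is that the laboratory can know the arm.

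Finally, masking the laboratory does not mask the analyst, and the Sponsor, which prepares the list, supplies one of the two products. That stands as a limit of the remedy. It is no reason to leave the product on the label.

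**Conclusion.** The concern holds. Section 10.3 gives the laboratory producing the primary-objective data information that can disclose the arm for all 40 planned specimens, and for more if enrolment exceeds 20. The field adds nothing to identification.

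The consequence is a risk of detection bias. Its size cannot be computed from the documents, which do not show that it would occur. An additive shift biases the comparison only where it differs between baseline and day 84; arm-related exclusion of specimens can bias it without any such shift.

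The conclusion rests on two assumptions: that the product field means the assigned product, and that no masking arrangement exists outside the documents. It should be fixed because it affects the primary objective and the remedy is nearly free. It is not shown to invalidate the study.

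**What to change.** In Section 10.3:
- Remove the product from the sample label and the shipping paperwork. Label with subject number and visit, or with a coded sample ID, only. Keep the visit.
- Limit the catch-all for other identifying information so that nothing disclosing the arm comes back through it.
- State that the Sponsor holds the randomization list and merges it with the qPCR data only after the laboratory has locked the Ct values and QC exclusions. Name who performs the product comparison; if it is the laboratory, release the key to it after that lock.

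The cost is one label field removed and a few lines of text. No subjects, visits, biopsies or assays are added, and the Sponsor already prepares the list that links subject to product.
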